7.1. Steering Committee

The Steering Committee (SC) is responsible for overseeing and maintaining the scientific and operational integrity of the project. Duties include approving the final trial protocol; overseeing the scientific direction of the trial; review and approval of case report forms, assessment questionnaires and manual of operations; review and approval of main analysis plan; review and vote on any proposed protocol amendments; review, comment on and vote on any presentations, publications or recommendations of the Publications sub-committee; and act on any recommendations from the DSMB

The SC will meet annually.

7.1.1. Publications Sub-Committee

A Publications subcommittee will be established, comprised of up to 4 individuals (two of which will be from the SC) who will initially meet quarterly to give direction and timelines to the expected writings, publications, presentations and pronouncements from this project. The publications committee will be responsible to review and comment on proposals for papers made by investigators, review trial press releases, approve secondary databases analyses, address any issues pertaining to authorship of publications and presentations, and ensure that NHLBI publications approval procedures are followed. It will also assist the research staff with registering the project with clinicaltrials.gov and establish a schedule for the submission of trial results to clinicaltrials.gov (within 12 months after study completion).

7.2. Project Management Team (Plan).

Under the guidance and leadership of the SC, the PMT will plan and implement/conduct the project in a manner that adheres to the approved protocol and manual of operations. The PMT will be established during month 1 or 2 of year 1 and meet in-person or via teleconference every 1-3 weeks. It will be led by the Project Manager (to be determined), in concert with the project PI. Any and all financial and operational issues that might require input from the full PMT will be added to the agenda for the next meeting of the PMT. The agenda will follow a standardized format for each meeting to address on-going business (screening report, enrollment report, retention report, assessments, process initiatives, and financial issues), new business, and action items.

Responsibilities for the PMT include, but are not limited to, telecommunication issues, patient education, data collection and entry, retention and adherence, maintenance of staff skills for testing, effective integration of both the center-based and hybrid programs, project

assessments, and protocol fidelity. Other PMT members will include the PI, the project's to-be-hired research coordinator, the Coordinator for CR at the Detroit campus, the registered dietician for the Detroit CR program, the hospital's Director of the Office of Performance Excellence and Quality or h/her designee, a behavioral medicine specialist, a former (recent) patient from our Detroit-based CR program, and a staff person from the System's Virtual Care Unit. *To ensure that the objectives of the trial are being met, the PMT will adopt an approach that is both proactive and rapid-response reactive.* The former approach will actively survey/identify potential "pinch-points" for trial operations (based on team planning discussions and experience gained from the years of operating CR, clinical trials in CR, and home-based CR) and design accordingly the study operations and schedule staff for the effective achievement of objectives. The latter approach (i.e., rapid-response reactive) involves both the regular review of operational report data (e.g., weekly enrollment reports, retention to follow-up testing, time elapsed between data collection and data entry) and collecting CR staff feedback on trial operations and milestone achievement. If problems are identified that threaten achievement of study objectives, the PMT will adjust trial procedures using a rapid-cycle, data-driven methodology.

7.2.1. Subject Recruitment and Retention and Staff Adherence [SRRSA] sub-committee

During month 11 of the project staff will begin the real-time tracking of key indicators of patient engagement in the study (e.g., adherence to testing). This will be done equally in both study groups to aid in identifying favorable/unfavorable implementation issues; it may include surveying and tracking the adoption and acceptability of changes to CR delivery by staff and patients, as well as assessing sustainability of the over-all model. A sub-committee of the PMT (called the *Subject Recruitment and Retention and Staff Adherence [SRRSA] sub-committee*) will be convened and charged with the above duties, as well as track, report and help intervene on other global project issues such as: ensuring convenient hours for testing, ensuring available hours for delivery of both CBCR and HYCR, ensuring equivalent delivery of educational content, and the timely completion of the patient's individual treatment plans. The SRRSA will also periodically (every 6 months) shadow-evaluate (using video and observation) CR staff for the uniform conduct of patient assessments and the uniform delivery of CR per protocol standards. Finally, the SRRSA committee will conduct a systematic, standardized rapid-cycle review of any patient (from either study group) that did not complete follow-up visit 1 testing or follow-up visit 2 testing. Learnings gathered from such will be applied to in a manner to avoiding future retention issues.

7.3. Data Safety Monitoring Plan/Board (DSMB) (See also Appendix A for additional details)

The Data Safety Monitoring Board (DSMB) for this trial will be an "internal DSMB", comprised of 4 individuals that are independent of the NHLBI, trial investigators and trial management. The NHLBI will approve the membership of the DSMB and the DSMB serves in an advisory capacity to both the NHLBI and the trial's Steering Committee. The DSMB will be comprised of two senior staff from within Henry Ford Health System, one of which will be a senior physician-scientist with NIH funding and the other will be a clinical cardiologist experienced with clinical trials from the Division of Cardiovascular Medicine (who will also serve as chairperson). The third DSMB member will be an external (to HFHS) cardiac

rehabilitation professional (clinical exercise physiologist) that is actively working in the field of CR. The fourth member will be a biostatistician (other than [name]) from the HFHS Department of Public Health Sciences. It will be the responsibility of the study coordinator and project manager, in conjunction with the [name], to ensure that unexpected SAEs associated with exercise training (defined as occurring during or within 3 hours after exercising) will be reported to the IRB and DSMB within 10 days of occurrence. The DSMB will meet bi-annually, of which a portion of each meeting will be with study investigators.

The primary endpoint for this study is number of CR sessions attended (versus a clinical endpoint such as death or re-hospitalization); therefore, the DSMB will not have to address the issue of trial continuation relative to clinical endpoint futility. All subjects will be evaluated for the specified duration of the trial for all primary and secondary outcomes measures. A subject's participation in the trial can also be stopped upon their formal request for withdrawal. The number of subjects that withdraw consent from trial participation will be tracked and reported to the DSMB.

The monitoring for unexpected major SAE's, as well as patient withdrawals, will occur continuously through the study by the project manager and research coordinator. The DSMB will meet every six months during the trial, and at the end of the trial, to review all trial-related reports and study findings. All records of AE and SAE will be available to the DSMB chair and the entire DSMB at any time, upon request.

All relevant unexpected and major SAE that occur during or within 3 hours after exercise will be collected, summarized and reported within 10 days to the local IRB and to the DSMB. Although the occurrence of these SAE's is extremely rare in the CR setting, any such events that do occur will be investigated and discussed jointly between the principal investigator and the DSMB or its chair. Any policy or procedural changes that arise from such discussion will be incorporated into a revised study protocol. Subjects that withdraw consent from trial participation will also be tracked by the study coordinator and reported to the DSMB.

The primary and secondary analyses will be conducted by [name] (biostatistician) from Public Health Sciences and he will possess a copy of the treatment codes for randomization.

8. Data Management

8.1. The data needed to test the primary hypothesis from this proposed project will be gathered from 270 subjects. The final data set will be comprised of demographic and clinical data gathered from questionnaire, electronic medical record, clinical CR care, and laboratory assessments. The three main time points for laboratory assessments are upon entry in to the trial, immediately after the patient completes CR (follow-up visit 1), and at 6 months after completing CR (follow-up visit 2). The primary outcome measure is attendance to CR; secondary outcome measures are quality of life and exercise capacity.

Data from the above mentioned sources will be collected on case report forms (CRFs) and entered in an ongoing manner (and within 2 weeks of collection) by the research assistant or staff from the Henry Ford Clinical Exercise Physiology Core Laboratory, and they will follow entry and validation processes that are consistent with the Health System's Department of Public Health Sciences (Research Informatics Unit). Study data will be collected in and then managed using REDCap (Research Electronic Data Capture, Vanderbilt University, Tennessee) electronic data capture tools (90). A thorough, study-specific data dictionary, defined by all members of the research team in an iterative, self-documenting process, will be compiled. The baseline data form and the final visit (follow-up visit 2) data forms will require the signature of [name].

The final data base will be stripped of identifiers (de-identified) and secured and hosted on a HIPAA-compliant server managed by the Department of Information Technology at the Corporate Data Center of Henry Ford Health System. REDCap will be used for generating the shared dataset. It will be used to remove identifiers, export data in a format that SAS can read, and create the SAS code needed to read the data in SAS. REDCap will also export PDF's of the case report forms and the data dictionary (codebook). The data base will be made available to the NHLBI. It will also be made available to others (upon request), under the auspices of a data sharing agreement that includes a commitment to (a) use the data for research purposes only, (b) not attempt to identify any one individual, and c) secure the data using appropriate computer technology and back-up. The dataset (and an accompanying data dictionary and other documentation) will be prepared to share in accordance with NHLBI data repository requirements, and consistent with other repository (BioLINCC) and NHLBI policy requirements.

9. Manual of Operations

A manual of operations (MOO) will be developed for all key aspects of the trial and will provide objectives, scope, design and operational policies and procedures beyond that spelled out in this clinical protocol. The manual will detail instructions for completing CRFs (e.g., baseline medical history data), baseline and follow-up questionnaire and clinical assessments, retrieval of primary endpoint data, and exercise training in CBCR and HYCR. The MOO will detail the follow-up testing/assessment schedule and survey tools, the follow-up phone calls to be completed at 2 and 4 months after completing CR, trial level contact information, and data queries. With regards to the CPX test and the 6 min walk test, quality assurance assessments/training, data handling/transfer, and any variable-specific data calculations or manipulations will be addressed in the existing manual of operations/procedures found within the CPX Core lab.

10. Statistical Analysis Plan

[name] (biostatistician) will oversee and conduct the data analysis for this trial. He will also assist with the development of enrollment and retention reports sent to the NHLBI and will also assist with preparing materials for the DSMB meetings that are held every 6 months.

10.1. Randomization Procedure

Using computer generated randomization, the randomization process will be stratified by race and sex and blocked to ensure balance at random accrual points. Lists were compiled for the 4 sex-race specific strata. As new participants are added to the study they will be assigned the next available treatment assignment (CBCR, HYCR) based on the lists provided. The project manager will be responsible for treatment assignment as all other staff involved in the study will be blinded as to the randomization lists to avoid bias.

10.2. Sample size and power calculations.

We propose to enroll a total of 270 patients evenly randomized into two groups of 135 patients each. To determine power for **Hypothesis 1**, we will use a Student's t-test approach. From recent data from our administrative CR data base, we believe that the CBCR group will complete 21 ± 13 (mean + sd) visits over the course of the study. The test, with a two-sided 0.05 alpha level, will have 80% power to detect an increase of 4.5 visits. We believe this to be a clinically significant difference (5).

Also, for **Hypothesis 2**, our recent administrative data indicates that 24% of patients in our CBCR program complete 36 visits. A chi-squared test with a two-sided 0.05 alpha rate and 135 subjects per group will have 80% power to detect an **increase to 39.8% or more in the HYCR group** (effect size=15.8 percentage point increase).

Hypothesis 3, 4 and 5 require longitudinal measures six months after CR is completed, so it is possible that some lost to follow-up will occur at follow-up testing point number 2. If we assume that no more than 20% will be lost, our sample size for this analysis will be at least 108. We anticipate a standard deviation of the change in meters walked in the 6-minute walk to be 107 meters (based on data from the Henry Ford Core Exercise Laboratory) When the sample size in each group is 108, a two group 0.05 one-sided t-test will have in excess of 90% power to reject the null hypothesis that the CBCR and HYCR groups are not equivalent (the difference in means is 50 meters or farther), in favor of the alternative hypothesis that the means in the two groups are equivalent.

The measured of peak VO₂ should have a standard deviation near 6 (86). With a sample size of 108 per group, a two-group one-sided t-test will have greater than 80% power to reject the null hypothesis that the CBCR and HYCR groups are not equivalent (the difference in means is 2.0 mL/kg/min or farther), in favor of the alternative hypothesis that the means in the two groups are equivalent.

Based on Campbell, et al. (87), we anticipate that the standard deviation of the Short Form Health Survey (SF-12) physical component summary will be 22 and the mental component summary will be 18. When the sample size in each group is 108, a two-group 0.05 one-sided t-test of the physical component scale will have 80% power to reject the null hypothesis that the

CBCR and HYCR are not equivalent (the difference in means is 7.5 or further from zero in the same direction), in favor of the alternative hypothesis that the means of the two groups are equivalent. The power for the mental component summary will exceed 90%.

10.3. Data Analysis Plan.

Data analysis will begin with preparatory activities such as checking for complete data entry, identification of outliers, and other such data cleaning tasks. Once the above tasks are completed, the data base will be “locked” for analyses. The Statistical Analysis System, (SAS, version 9.4) will be used for data analysis. A detailed descriptive analysis of all quantitative data will be performed involving the summarization of data and the use of inferential and graphical exploratory analytic techniques. The information obtained from this preliminary investigation will be used to: 1) describe univariate and bivariate sample distributions of the data; 2) identify the interrelationships between variables (i.e., need for covariate adjustment); and 3) check for violations of assumptions underlying identified statistical techniques (e.g. independence, linearity, homoscedasticity, normality). In the event that statistical assumptions are severely violated, data transformations or nonparametric methods will be employed. An intention to treat approach will be utilized for all analyses. For hypothesis 1 the number of visits completed before lost to follow up will be used and for hypothesis 2 a yes/no response will be generated based on the observed data.

R33- Primary Aim: Assess the effect of a HYCR program on over-all patient attendance

For the **Primary Hypothesis** (number of sessions completed), if the distribution of the number of sessions completed is normal then a Student’s t-test will be used for comparison of the two groups. In the likely event it is skewed a two-sample Wilcoxon with a Fligner-Policello correction for unequal variances will be used. **Hypothesis 2** (percentage of patients completing 36 CR sessions) will be addressed using a Chi-squared test for comparison of proportions.

R33- Secondary Aim: Assess the effect of HYCR on exercise capacity and quality of life.

Hypotheses 3 and 4 (both address measures of exercise capacity) and **Hypothesis 5** (QOL) all involve assessing if the two group responses are equivalent. A two one-sided test approach will be used to demonstrate equivalence between the two groups.

There are several identified **exploratory aims** for this project, including but not limited to:

- (a) short-term (6 month) retention of CR-related outcomes [e.g., exercise capacity, QOL, and self-engaged (not CR) purposeful exercise and total physical activity habits]
- (b) program cost effectiveness.

Analyses of the exploratory aim associated with the short-term retention of CR-related outcomes will be analogous to the analyses described above, such that Student's t-test, Chi-squared tests or their nonparametric alternatives will be utilized.

Concerning cost effectiveness, we have included it as an exploratory aim because some view a home- or hybrid approach to CR (with or without telemedicine) as a "negative" financial business model due to lack of revenue (and increased patient care expenses and staff time). The cost effectiveness of the HYCR program will be explored to determine the cost differential between the two CR approaches. In both CR models we will collect and calculate costs associated with program implementation (staff time, HR monitors, and upgrading desk tops for telemedicine) as gathered from both administrative data within the CR unit and from the Health System's Corporate Financial Services Department. We will also collect costs from participants at follow-testing, including direct nonmedical and medical costs (including value of time of the participants attending a program, waiting, and travel). In collaboration with our colleagues at both Health Alliance Plan and Blue Cross and Blue Shield of Michigan, the two Michigan-based insurers that agree to cover hybrid CR for their subscribers in this project, we also have the unique opportunity to partially track and compare the potential impact of HYCR and CBCR on health care utilization and costs during the 6 months after CR is completed (and afterwards).

Finally, the CR-outcomes and behaviors that Henry Ford normally assesses before and immediately after CR (e.g., Rate Your Plate, Dartmouth COPOP for QOL) will again be assessed at the 6 month post-program follow-up 2 visit (for short-term retention). In addition, reasons for stopping program attendance before completion of the study recommended 36 visits will be gathered from all subjects for subsequent secondary analysis.

11. Institutional Review Board and Ethics and Good Clinical Practice

This study must be carried out in accordance with the approved protocol and all Henry Ford Health System and study operating procedures. Compliance with such protocols and procedures will ensure adherence to good clinical practice.

Before implementing the study, the final protocol, the proposed informed consent and other subject information documents must be reviewed and approved (initially and then annually) by the System's Institutional review Board (IRB). A signed and dated document that the protocol and informed consent have been approved by the IRB must be in-place before study initiation. Any amendments to the protocol, other than administrative, must be approved by the IRB.

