4.3.1. Study Population

270 patients with an index event that qualifies for CR will be recruited (a) prior to discharge from the hospital, (b) soon after hospital discharge with documented referral to CR, or (c) from screening appointment schedules for physicians that will be seeing patients in an

ambulatory care setting. The inclusion and exclusion criteria are not overly restrictive, such that we expect a sufficient number of patients eligible and enrolled in CR to consent to trial participation.

4.3.1.a. Inclusion Criteria

- 1) Has agreed to participate in CR and has experienced a cardiac event (myocardial infarction, coronary revascularization, heart valve surgery, or cardiac transplant in the past 6 months; diagnosed with chronic, stable AHA/ACC stage B or C heart failure or Canadian class 0-2 stable angina pectoris)
- 2) Lives in or plans to remain in the greater Detroit, MI area for the next year
- 3) Age 18-85 years of age
- 4) Agrees to attend at least one CBCR session
- 5) Agrees to scheduling at least 2, up to 3, CR sessions (either CBCR or HYCR)/wk
- 6) Has demonstrated to research staff their ability to access and connect to the internet via smart phone or tablet and already has access to satisfactory home- or community-based exercise equipment

4.3.1.b. Exclusion Criteria

- 1) Received a left ventricular assist device, receiving continuous inotropic support (e.g., milrinone), or undergoing hemodialysis
- 2) Angina at rest or with a low functional capacity (< 2 METs)
- 3) Advanced cancer, advanced risk for falling, limiting cognitive impairment, or other advanced disorder that limits participation in CR
 - a. Advanced risk for falling will be assessed by 5X sit-to-stand test, with a cut-off score of >15 seconds
 - b. Cognitive assessment will be completed using the Mini-Cog instrument, with a cut-off score < 3 used to exclude potential subjects.
- 4) Severe arrhythmia unless adequately treated (e.g., implantable cardiac defibrillator)
- 5) Pregnant or plan to become pregnant in the next year.
- 6) Major cardiovascular procedure or hospitalization planned in the next 6 months
- 7) Exercise testing results that preclude safe exercise training, including abnormal blood pressure response, early ischemic changes or unexpected life-threatening arrhythmia
- 8) Participation in another clinical trial that interferes with iATTEND participation, follow-up, data collection, exercise capacity or quality of life.

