4.3.3. Subject Enrollment

4.3.3.a. Screening ... from in-patient and EMR

Using census data from the EMR for in-patient cardiology units, as well as the out-patient preventive cardiology unit work que in the EMR, potential subjects will be identified/screened by the CR and research staff that visits or calls patients. The names of potential candidates will be forwarded to the research staff who will then conduct a detailed screening of eligibility using the EMR and a telephone call. If the patient meets the enrollment criteria and agrees to participate after having discussed study purpose, procedures, risks and responsibilities, a baseline appointment will be made, ideally on the same day the patient will be scheduled to attend CR orientation; 7-14 days after discharge if hospitalized. Patients stating interest in the research study will meet with the research coordinator, the project PI, or the project manager to undergo further screening and receive a verbal explanation of the trial and sign informed consent.

4.3.3.b. Baseline Clinic Visit

The baseline testing required in this protocol should be completed as soon as possible after signed consent, but may be completed up to 4 weeks after consenting, if necessary. All baseline testing will be completed prior to a patient's first session in CR. For any study visit that includes a QOL assessment and a symptom-limited cardiopulmonary exercise (CPX) test, the quality of life (QOL) instrument(s) (Dartmouth COOP, and/or EuroQOL-5D) must be completed prior to the CPX test. Also, the 6 min walk (6MW) test must be completed, per standardized procedures (84), 1 hour or more before the CPX test; therefore, during any clinic visit the order of these tests is as follows: (a) 6MW, (b) QOL tools and other assessments (PHQ-9, Rate your Plate, mini-cog), (c) 5x repetition sit-to-stand test, and (d) CPX test. The 6MW and the CPX test will be completed per procedures as specified and overseen by the Henry Ford Clinical Exercise Physiology Core Laboratory ("Exercise Core Lab"); and case report forms for 6MW and QOL surveys and data collected from the CPX test will be forwarded to the Exercise Core lab or data entry/management as indicated.

4.3.3.c. *Baseline Testing*

The written questionnaires (EuroQOL-5D, Dartmouth COOP, Rate Your Plate, and PHQ-9) will be administered per the standardized instructions associated with each instrument.

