4.3.4. Randomization

After a patient has satisfied all enrollment criteria, informed consent obtained, and they complete all of the written and exercise assessments, the patient will be randomized to usual care CR or Hybrid CR. **Generally, randomization should occur the same day of the final screening test (i.e., CPX).** A one-to-one randomization scheme will be computer generated and will be balanced on random accrual points and stratified by race and gender.

4.3.5. Study groups.

Patients in both arms of iATTEND will receive CR. Participation in CR will begin as soon as possible after randomization, with a goal of initiating training no more than 10 days after randomization.

4.3.5.a. Usual care. Patients in this arm of the trial will receive the following:

1. Industry standard, facility-based CR, in accordance with current Henry Ford policies and procedures; attending CR 2-3 days per week. Briefly, transportation issues will be resolved per current practices using family and community resources. Individual treatment plans (ITPs) will be established upon enrollment into CR; revised per patient progress; and uploaded in to the EMR upon entry and 30, 60, and 90 days and upon completion of CR. Current guidelines for prescribing exercise (type, frequency, duration, intensity) will be in accordance with Unit procedures, as adapted from published guidelines (85). Any ECG telemetry or blood pressure measurement during exercise will be used as clinically indicated, and in accordance with program policies and procedures. Health insurance coverage will be verified per Unit protocol and CR visits billed in accordance with a patient's policy and per hospital practices. To avoid any effect that co-payments or differing co-payment amounts might have on attendance (and thus induce a potential source of bias between groups), all co-payments will be charged to the project. For those patients without health insurance, their CR sessions will be charged to proposed project budget. CBCR subjects will be encouraged to engage in purposeful exercise ad libitum on their own each week.

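### The project manager, the one operational role not blinded to the randomization lists (10.1), may also screen patients and take consent (4.3.3.a)

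*Combined protocol and SAP*

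**What the plan says.** Section 10.1 says that lists have been compiled for the four sex-by-race strata and that, as participants join, "they will be assigned the next available treatment assignment (CBCR, HYCR) based on the lists provided". On who holds the lists it says: "The project manager will be responsible for treatment assignment as all other staff involved in the study will be blinded as to the randomization lists". The stated purpose of that blinding is to avoid bias.

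Section 4.3.3.a says that interested patients meet the coordinator, or else "the project PI, or the project manager to undergo further screening and receive a verbal explanation of the trial and sign informed consent". Section 4.3.4 places randomization after eligibility, consent and all baseline assessments, generally on the day of the last screening test, and balances the 1:1 scheme at random accrual points. Section 7.3 adds that the trial biostatistician holds a copy of the treatment codes; no enrolment duty is given to that role.

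**The concern.** Allocation concealment requires that whoever decides on, or influences, a patient's entry does not know what that patient would receive. Section 10.1 recognizes this by blinding the other staff to the lists. Section 4.3.3.a then admits the one operational role outside that blinding to the screening and consent conversation.

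This trial is exposed to the problem for two reasons. The arms cannot be masked from patients or staff. The primary endpoint, sessions completed within 6 months, depends on motivation and circumstances that a person explaining the trial can partly judge. A person who knows the next entry could, even without intending to, encourage one patient more than another or take consent sooner or later. Any resulting difference between arms would count as a treatment effect in the primary comparison.

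**Working it through.** **The text, side by side**

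| Question | Section | Answer |
|---|---|---|
| Who assigns and can see the lists? | 10.1 | Project manager; other staff are blinded |
| How is an assignment taken? | 10.1 | Next entry on a pre-compiled stratum list |
| Who may screen further and take consent? | 4.3.3.a | Coordinator, PI or project manager |
| Is the project manager barred from enrolling? | 4.3.3, 4.3.4, 7.2, 10.1, 11.1 | No; 11.1 allows the PI or a designee to explain the trial |
| Is the next entry hidden from the list holder? | 4.3.4, 9, 10.1 | No such measure is described |

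Random accrual points make the sequence hard to guess for someone without the list, but they hide nothing from someone who has it. The order in 4.3.4 governs when an assignment is made, not who can see it beforehand.

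**Illustration of what an imbalance would do (t-test)**

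Inputs from section 10.2: SD 13 visits, 135 per arm, two-sided alpha 0.05.

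- SE = 13 × √(2/135) = 1.582; df = 268; critical value 1.969.
- Check against the plan: a 4.5-visit difference gives 80.9% power, which agrees with the stated 80%.
- Under no treatment effect, a trial-wide imbalance of b visits gives a non-centrality of b/1.582.

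| Imbalance b (visits) | Type I error, t-test | Type I error, Fligner-Policello (simulated) |
|---|---|---|
| 0.3 | 5.4% | 5.5% to 5.8% |
| 0.5 | 6.1% | 6.1% to 6.3% |
| 1.0 | 9.7% | 9.6% to 10.2% |

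The last column uses the test that section 10.3 expects to need, and the ranges are across repeated simulation runs. The outcome is 24% at 36 visits (section 10.2), with the rest beta-binomial on 0 to 35 (a = 0.680, b = 0.783), giving mean 21.0 and SD 13.0. Selection replaces a fraction p of HYCR values with the larger of two draws, and the same fraction of CBCR values with the smaller. Each replacement shifts the mean by 7.37 visits, so p = b/(2 × 7.37) = 0.020, 0.034 and 0.068. With no imbalance the simulated error is 5.1% to 5.2%.

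**How much selection that requires**

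Trial-wide imbalance = share of patients the project manager handles × imbalance among them. Both factors are assumptions.

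- One third handled, 3-visit imbalance: 1/3 × 3 = 1.0 visit. Three visits is two thirds of the planned effect (3/4.5).
- One tenth handled, same imbalance: 0.1 × 3 = 0.3 visit.

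**Does the delay between consent and randomization break the link?**

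Accrual is 270 patients over the 30-month enrolment period in section 4.2, or 9 per month. The mean gap between randomizations in a stratum is 30 × 30.44/(270 × share) days. With Poisson arrivals (assumption), the chance that the entry next in line at consent is still next d days later is exp(−d/gap).

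| Stratum share (assumption) | Mean gap | 1 day | 7 days | 28 days |
|---|---|---|---|---|
| 25% (equal strata) | 13.5 days | 93% | 60% | 13% |
| 40% (about 80% African American as in section 3.5, sexes equal) | 8.5 days | 89% | 44% | 4% |

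On the prompt schedule that the protocol prefers, delay protects little. At the 4-week limit it protects well.

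**The case against.** The overlap is a permission, not a plan. The project manager is one of three alternatives, and nothing says how often, if ever, that person will take consent. The form of the lists is not described, so sight of upcoming entries is inferred from the wording of 10.1. These points limit the likelihood of harm but do not remove the overlap.

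Other features narrow the opportunity:

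- Research staff pre-screen by record review and telephone; for anyone who "meets the enrollment criteria and agrees to participate after having discussed study purpose, procedures, risks and responsibilities, a baseline appointment will be made". Much of the decision to join is therefore made before the consent meeting.
- Some criteria leave little room for judgement. Falls risk and cognition have numeric cut-offs, and for equipment the patient "Has demonstrated to research staff their ability to access and connect to the internet". Exercise testing is overseen by the core laboratory (4.3.3.c).
- Baseline testing "should be completed as soon as possible after signed consent, but may be completed up to 4 weeks after consenting, if necessary", so another patient may take the entry first.
- Section 4.5 instructs staff not to influence attendance differentially, and a sub-committee monitors this. That concerns conduct during rehabilitation and does not conceal the list.
- Section 10.3 looks at the need for covariate adjustment. Imbalance in measured baseline factors could be seen and adjusted for; unmeasured motivation could not.
- Section 9 promises more detail: "A manual of operations (MOO) will be developed for all key aspects of the trial". Randomization and concealment are not among the topics it lists, and a manual would not withdraw a permission that the protocol gives.

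The illustrative error rates rest on assumed shares and imbalances. The simulation also supposes that future attendance is ranked perfectly among the selected patients. They show scale only, and the case for the change does not depend on them. What remains is encouragement and timing at the consent meeting by someone who may know the next assignment.

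**Conclusion.** The concern holds as a gap in allocation concealment: as written, the protocol lets the one operational role not blinded to the lists screen patients and take consent. This rests on the plain reading of 10.1 that the project manager can see upcoming entries. It is not a finding that bias is likely, and no size can be derived from the documents. If the project manager handles about a tenth of patients, even a 3-visit imbalance among them leaves the error rate near nominal. At a third of patients, the same imbalance roughly doubles it. The gap should be closed because selection on unmeasured motivation at entry cannot be repaired in the analysis, and prevention costs very little.

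**What to change.** 1. In 4.3.3.a, remove the project manager from the roles that carry out further screening and take consent. The coordinator and the PI remain.
2. In 10.1, add: *Each assignment is released singly, by a person or system not involved in screening or consent, after eligibility, consent and baseline assessments have been recorded for that patient.*

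The order of steps is already in 4.3.4; the separation of roles, the prior recording and the single release are new. The added sentence also closes the routes left by the designee wording in 11.1 and by the general reference to research staff in 4.3.3.a. The project manager can keep the assignment task, so same-day randomization is unaffected.

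Cost: one deletion and one sentence, about 9 release requests a month (270/30), and no new staff. The drawbacks are slightly less flexibility in who takes consent and the need for a non-enrolling deputy when the project manager is away.
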